6.4. Covariates

Candidate covariates for the development of Serious infections (including Tuberculosis, Pneumonia, Pneumocystis pneumonia, Sepsis, and Opportunistic infection), Herpes zoster, and Malignancy considered in this study are shown below.

| Covariate | Serious infections | Herpes zoster | Malignancy |
|--------------------------------------|-----------------------|------------------|------------|
| Gender [reference: male] | 0 | 0 | 0 |
| Age [reference: <50 years] | 0 | 0 | 0 |
| Body weight [reference: <50 kg] | 0 | 0 | 0 |
| BMI [reference: <18.5 kg] | 0 | 0 | 0 |
| Duration of UC [reference: <2 years] | 0 | 0 | 0 |

NIS Protocol A3921248 Statistical Analysis Plan

Serious Herpes Covariate infections Malignancy zoster Severity of UC [reference: moderate] 0 Past history (Infections) [reference: absent] 0 0 Past history (Malignancy) [reference: absent] × X Past history (Lung disorder) [reference: absent] 0 × × Complications (Infections) [reference: absent] 0 0 X Complications (Malignancy) [reference: absent] 0 Complications (Hepatic function disorder) [reference: absent] 0 0 0 Complications (Hepatitis B) [reference: absent] X X 0 Complications (Hepatitis C) [reference: absent] X X 0 Complications (Renal impairment) [reference: absent] 0 \circ 0 Complications (Diabetes mellitus) [reference: absent] Ο 0 0 Smoking [reference: absent] 0 0 0 Family history of malignancy (including lymphoma) [reference: absent] Prior treatment with a 5-aminosalicylic acid preparation [reference: 0 0 0 absent] Prior treatment with steroid [reference: absent] 0 0 0 Prior treatment with an immunomodulator (azathioprine, 0 0 6-mercaptopurine) [reference: absent] Prior treatment with tacrolimus [reference: absent] Prior treatment with a biologic agent [reference: absent] 0 0 Baseline neutrophil count [reference: <2000/µL] 0 0 0 Baseline lymphocyte count [reference: <1000/μL] 0 0 \circ Prior vaccination with a herpes zoster vaccine [reference: absent] 0 0 × Prior vaccination with a pneumococcal vaccine [reference: absent] 0 Prior vaccination with a tuberculosis vaccine [reference: absent] 0 Prior vaccination with a pneumocystis jirovecii pneumonia vaccine [reference: absent] Prior vaccination with a hepatitis B vaccine [reference: absent]

o: Applied, ×: Not applied

Additional covariates may be included or some deleted after consideration based on an interim analysis of this study or emerging knowledge. If this will occur, this SAP will be revised.

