With regard to analyses that involve the time to onset of each element in the safety specification, if development of an event has been reported in a patient but its onset date is unknown, the onset date will be imputed with the last date on which the patient can be confirmed to be free from the event in view of all kinds of data collected; the shortest possible date imputed may be the start date of treatment. For patients in whom development has not been reported but the date of the end of observation is unknown, the end date will be imputed with the last date on which administration of this drug can be confirmed in view of all kinds of data collected; the shortest possible date imputed may be the start date of treatment.

Missing data (including the case of "unknown") for candidate covariates (Section 6.4) will not be imputed in univariate analyses. For multivariate analyses, missing data for candidate covariates will be treated as a subcategory of the category "unknown".

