8.1.3. Binary variables

For binary variables, patients included in each binary category will be summarized in terms of n and proportion. The two-sided 95% confidence interval (CI) will be determined using an exact method if a CI should be determined for the proportion.

When comparisons of the proportion should be made between subgroups, their risk ratios (RRs) will be presented with corresponding 95% CIs. Each RR and its 95% CI will also be presented graphically (See Appendix 2).

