To evaluate the dose-response relationship concerning the safety of the treatment with this drug, the following analyses will be performed in the patients treated at a higher dose level defined in Section 5.4.1 and in the patients treated at a lower dose level. To eliminate the effect of including patients who discontinued treatment during the induction phase, similar analyses will also be performed in patients treated at a higher dose level for a long term and in patients treated at a lower dose level for a long term:

• Adverse reactions of each element in the safety specification will be summarized in terms of number and proportion of patients as well as incidence and its 95% CI. In addition, the risk ratio and risk difference with their 95% CI will be presented for the patients treated at a higher dose level compared with those at a lower dose level.

• Adverse reactions will be summarized by SOC and PT in terms of number and proportion of patients.

In addition, to investigate the temporal change in the risk of the occurrence of each event, the following analyses will be performed in the patients treated at a higher dose level and patients treated at a lower dose level:

[figure not shown]
- Patients who experienced adverse reactions of each element in the safety specification will be summarized by timing of first onset, in terms of n and proportion as well as incidence and its 95% CI. As for the denominator to calculate the proportion, the denominator to calculate the incidence, and the categories used for onset timing, the corresponding descriptions in (1) should be followed.
- A Kaplan-Meier plot will be presented for the time to first onset of any adverse reaction included in each element in the safety specification.

• Subgroup analyses regarding patient characteristics

According to Section 8.1.3, the risk ratio based on the proportion of patients who experienced adverse reactions of each element in the safety specification will be determined and graphically presented for different subgroups regarding each of the patient factors defined in Section 8.2.2 in which events developed in ≥ 10 patients. Risk ratios will not be calculated for subgroups in which events developed in < 10 patients.

For each relevant subgroup defined in Section 5.4.2, patients who experienced adverse reactions will be summarized by SOC and PT in terms of n and proportion.

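### SAP 6.4 and 7 prepare a multivariable risk-factor analysis that Section 8 never specifies, leaving only crude one-factor risk ratios on proportions

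*SAP*

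**What the plan says.** SAP 6.4 opens with "Candidate covariates for the development of Serious infections" and goes on to herpes zoster and malignancy. It tabulates about 30 covariates, each with a reference level such as "Age [reference: <50 years", and marks which apply to which outcome.

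SAP 7 then sets two missing-data rules. Missing values "for candidate covariates (Section 6.4) will not be imputed in univariate analyses". The second rule begins "For multivariate analyses, missing data for candidate covariates will be treated as a subcategory" and assigns such values to an unknown category.

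SAP 8.1 provides summary statistics, proportions with risk ratios, person-year incidence with an exact interval, and Kaplan-Meier plots. For subgroup comparisons of proportions, 8.1.3 says "their risk ratios (RRs) will be presented with corresponding 95% CIs". It names no regression, stratification or adjustment.

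SAP 8.2.3.3 applies that ratio to each patient factor of 8.2.2: "the risk ratio based on the proportion of patients who experienced adverse reactions of each element in the safety specification will be determined". A filter follows: "Risk ratios will not be calculated for subgroups in which events developed in < 10 patients".

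Protocol 7.7.2.1 says that factors affecting adverse reactions will be examined by subgroup analyses on patient background. SAP 2.1 repeats this and states that data are collected only until discontinuation.

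**The concern.** The SAP names covariates, fixes reference levels and says how missing values enter a multivariate analysis, but gives no outcome model, adjustment set, selection rule or minimum event count. SAP 3 says the final analysis covers everything the SAP defines. An analyst could not run this part without designing it after the data are in.

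What the plan does specify has two weaknesses for judging risk factors.

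- **Overlap.** Age, disease duration, severity, prior steroid and prior biologic plausibly go together. A crude ratio credits each factor with part of the others' effect, so an inert factor can look harmful and a real one can be hidden.
- **Exposure.** The ratio compares proportions. If patients with a factor stop treatment sooner, they are observed for less time and have fewer chances to record an event.

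The protocol intends the results for proper-use material (section 5) and for review of risk minimisation activities (section 10). A misattributed factor could reach both.

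**Working it through.** **1. Is the analysis present anywhere?** Setting the sections side by side:

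| SAP section | Content on patient factors |
|---|---|
| 6.4 | Covariates and reference levels for three outcomes |
| 7 | Missing-data rules for univariate and multivariate analyses |
| 8.1.1–8.1.5 | Summaries, crude risk ratio, person-year incidence, Kaplan-Meier |
| 8.2.3.3, patient characteristics | One-factor risk ratios (8.1.3), plus SOC/PT tables |
| 8.2.3.3, dose | Incidence, risk ratio, risk difference, Kaplan-Meier, all unadjusted |

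The legible covariates of 6.4 all reappear among the 8.2.2 factors, so each does receive a one-factor ratio, subject to the 10-patient filter. That is a univariate analysis, and the univariate rule of SAP 7 has something to attach to. The multivariate rule has nothing.

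**2. The plan's own sample-size figures.** 470 / 0.95 = 494.7, rounded up to 495, as stated. With the exact interval of 8.1.4, a true rate of 8 and a limit of 4 per 100 person-years, the smallest exposure reaching 80% is 282 person-years (at least 19 events, probability 80.1%). This matches 470 patients if mean exposure is 282 / 470 = 0.60 years, which the documents do not state. The most that 60 weeks allows is 60 / 52.18 = 1.15 years.

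**3. Expected zoster events**, 470 × mean years × 0.08:

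- 0.60 years: 22.6, about 23
- 1.15 years: 43.2, about 43

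The 8.2.3.3 ratios count only events judged related to the drug, so the usable number may be lower.

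**4. What model can that support?**

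- The 13 covariates legibly marked for all three outcomes need at least 20 coefficients with the 8.2.2 categories: 22.6 / 20 = 1.1 to 43.2 / 20 = 2.2 events per coefficient. The full list cannot be fitted.
- Age in three levels (2), sex (1) and one binary covariate (1) make 4 parameters: 22.6 / 4 = 5.6 to 43.2 / 4 = 10.8 events each.
- Adding prior biologic makes 5: 22.6 / 5 = 4.5 to 43.2 / 5 = 8.6.
- A covariate with more levels, or an unknown category, lowers these further.

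**5. Possible size of confounding (all inputs assumed).** Factor A has no effect. Factor B has true risk ratio R and is present in a share pa of patients with A and pb of those without. Crude ratio for A = (1 + pa(R − 1)) / (1 + pb(R − 1)).

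| R | pa vs pb | Crude ratio for A |
|---|---|---|
| 2 | 30% vs 20% | 1.30 / 1.20 = 1.08 |
| 2 | 60% vs 20% | 1.60 / 1.20 = 1.33 |
| 2 | 70% vs 20% | 1.70 / 1.20 = 1.42 |
| 3 | 30% vs 20% | 1.60 / 1.40 = 1.14 |
| 3 | 70% vs 20% | 2.40 / 1.40 = 1.71 |

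**6. Possible size of the exposure effect (deliberately extreme assumption).** Take the same zoster rate, 8 per 100 person-years, in two subgroups, one observed 0.6 years per patient and the other 1.15. The proportions are 1 − exp(−0.048) = 4.7% and 1 − exp(−0.092) = 8.8%. Their ratio is 0.53, although the rates are equal.

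**The case against.** The other side has a good deal to say.

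- **Univariate analysis exists.** A reader might infer that Section 8 contains no risk-factor analysis and that the 6.4 covariates go unused. The documents do not support that: the 8.2.3.3 ratios reach them through 8.2.2. Only the multivariate part is missing.
- **No protocol breach.** The protocol promises subgroup analyses, and 8.2.3.3 delivers them. Neither document promises adjusted estimates.
- **Other evidence exists.** The crude ratios are not the only information on who is at risk. There are also SOC/PT tables by subgroup, dose comparisons, and counts by concomitant immunosuppressant or CYP inhibitor use. None is adjusted.
- **Multiplicity is separate.** One might multiply 76 categorical factors by 13 safety elements (76 × 13 = 988) and expect 5%, about 49, to exclude 1 by chance. That count precedes the 10-patient filter, treats overlapping elements and nested factors as separate, and would not be cured by adjustment. It carries no weight here.
- **The sentence may be a remnant.** The revision history records that part of the multivariate description was removed. Deleting 6.4 and the leftover sentence, and labelling the ratios unadjusted, would also restore consistency.
- **Adjustment has limits.** Events are few, and prior biologic use may lie downstream of disease duration or severity, so adjusting for it could hide a real factor.

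All of this stands. It narrows the point and keeps the remedy small. It does not explain how the multivariate rule now in SAP 7 is to be carried out, or remove the exposure problem in the crude ratios.

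**Conclusion.** The concern holds as an internal gap in the SAP. A multivariable analysis is prepared in 6.4 and 7 and never specified in 8, and what remains is crude ratios of proportions that account for neither overlap nor exposure time.

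The actual bias is unknown, because the documents give no correlations between factors and no discontinuation pattern by subgroup. The 1.1 to 1.7 range and the exposure example show what could happen under assumed inputs; they are not estimates for this study. The event range of 23 to 43 rests on the SAP's assumed zoster rate and an assumed mean exposure of 0.6 to 1.15 years.

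It would go too far to conclude that the subgroup results are invalid or that adjusted estimates should replace them. With so few events, the adjusted ratio belongs beside the crude one. This is a worthwhile, low-cost improvement.

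**What to change.** Add to SAP 8.2.3.3:

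- **Outcomes:** herpes zoster and serious infections; malignancy only if at least 10 patients have it.
- **Model:** for each 6.4 covariate marked for that outcome, a Poisson model with the 8.1.4 person-time as offset (uncapped for malignancy, as 8.1.4 provides), or a Cox model.
- **Adjustment:** a short fixed set such as age and sex. Add prior biologic only as a sensitivity adjustment.
- **Estimation:** Firth penalisation throughout, given the few events per parameter.
- **Reporting:** the adjusted rate ratio with its 95% CI beside the crude risk ratio, both exploratory. Label all other 8.2.2 ratios as unadjusted screening.

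If the sponsor no longer intends any multivariable analysis, the minimum is to remove 6.4 and the matching sentence in 7 and label every patient-factor ratio as unadjusted.

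The cost is SAP wording and a few models on data already collected. The downside is that adjusted estimates will be imprecise where events are few.

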8.2.4. Effectiveness analyses

In this study, the proportion of patients who achieved the remission based on the partial Mayo score will be the primary effectiveness endpoint.

8.2.4.1. Effectiveness assessment based on the partial Mayo score

• Proportions of patients who achieved study endpoints based on the partial Mayo score

The proportion of patients who achieved each study endpoint based on the partial Mayo score (remission or clinical response) will be calculated with its 95% CI for each study visit. The definition of the study visits should follow "10.1. Appendix 1: Details of Data Handling".

The definition of the endpoints based on the partial Mayo score is shown in Table 1.

Table 1. Endpoints Based on the Partial Mayo Score

| Endpoint | Definition |
|----------------------|---|
| Remission based on | The patient is called to have achieved remission if they meet all the following criteria: |
| the partial Mayo | ● Partial Mayo score ≤2 |
| score | • Stool frequency subscore ≤1 |
| | • Rectal bleeding subscore ≤1 |
| | • Physician's global assessment subscore ≤1 |
| Clinical response | • The decrease from baseline in the partial Mayo score ≥2 |
| based on the partial | |
| Mayo score | |

• Changes in the partial Mayo score

Summary statistics will be presented for each study visit regarding the partial Mayo score and the change from baseline in the partial Mayo score. For the change from baseline, its 95% CI will also be presented. The definition of the study visits should follow "10.1. Appendix 1: Details of Data Handling".

8.2.4.2. Effectiveness assessment based on the Mayo score

• Proportions of patients who achieved the responses based on the partial Mayo score

The proportion of patients who achieved each response based on the Mayo score (remission, mucosal healing, clinical response, clinical remission, endoscopic response, endoscopic remission, symptomatic remission, or deep remission) will be calculated with its 95% CI for each study visit. The definition of the study visits should follow "10.1. Appendix 1: Details of Data Handling".

The definition of the endpoints based on the Mayo score is shown in Table 2.

Table 2. Endpoints Based on the Mayo Score

| Endpoint | Definition |
|-------------------|---|
| Remission | The patient is called to have achieved remission if they meet all the following criteria: |
| | • Mayo score ≤2 |
| | • All Mayo subscores ≤1 |
| | • Rectal bleeding subscore = 0 |
| Mucosal healing | • Findings of flexible sigmoidoscopy subscore ≤1 |
| Clinical response | The patient is called to have achieved clinical response if they meet all the following |
| | criteria: |
| | • The decrease from baseline in the Mayo score ≥3 and ≥30% |
| | • Rectal bleeding subscore ≤1 or the decrease from baseline in the rectal bleeding |
| | subscore ≥1 |

NIS Protocol A3921248 Statistical Analysis Plan

Table 2. Endpoints Based on the Mayo Score

| Endpoint | Definition |
|--------------------|--|
| Clinical remission | The patient is called to have achieved clinical remission if they meet all the following |
| | criteria: |
| | • Mayo score ≤2 |
| | • All subscores ≤1 |
| Endoscopic | • The decrease from baseline in the findings of flexible sigmoidoscopy subscore ≥1 |
| response | |
| Endoscopic | • Findings of flexible sigmoidoscopy subscore = 0 |
| remission | |
| Symptomatic | The patient is called to have achieved symptomatic remission if they meet all the |
| remission | following criteria: |
| | • Mayo score ≤2 |
| | • All subscores ≤1 |
| | • Rectal bleeding subscore = 0 |
| | • Stool frequency subscore = 0 |
| Deep remission | The patient is called to have achieved deep remission if they meet all the following |
| | criteria: |
| | • Mayo score ≤2 |
| | • All subscores ≤1 |
| | • Rectal bleeding subscore = 0 |
| | • Findings of flexible sigmoidoscopy subscore = 0 |

• Changes in the Mayo score

Summary statistics will be presented for each study visit regarding the Mayo score and the change from baseline in the Mayo score. For the change from baseline, its 95% CI will also be presented. The definition of the study visits should follow "10.1. Appendix 1: Details of Data Handling".

8.2.4.3. Effectiveness assessment based on individual Mayo subscores

• Changes in each Mayo subscore

Summary statistics will be presented for each study visit regarding each Mayo subscore and the change from baseline in the Mayo subscore. For the change from baseline, its 95% CI will also be presented. The definition of the study visits should follow "10.1. Appendix 1: Details of Data Handling".

8.2.4.4. Changes in faecal calprotectin

Summary statistics will be presented for each study visit regarding the faecal calprotectin level and the change from baseline in the faecal calprotectin level. For the change from baseline, its 95% CI will also be presented. The definition of the study visits should follow "10.1. Appendix 1: Details of Data Handling".

8.2.4.5. Subgroup analyses

For each relevant subgroup defined in Section 5.4.2, the proportion of patients who achieved the remission based on the partial Mayo score at the end of treatment will be analyzed.

9. LISTINGS

The following patients and events will be listed in tabular form:

- Patients included in the study
- Patients who experienced AEs
- Patients who experienced adverse reactions
- Patients excluded from the safety analysis who experienced adverse reactions
- Patients with a contraindication to this drug who experienced adverse reactions
- Patients who experienced serious adverse reactions
- Patients who experienced SAEs
- Patients with hepatic impairment who experienced adverse reactions
- Patients with renal impairment who experienced adverse reactions
- Aged patients who experienced adverse reactions
- Events included in the scope of the safety specification
- AEs considered as out of collection-period

The following documents required for application of re-examination (of which forms are presented in PSEHB/PED Notification No. 1128-2 issued by the Director of the Pharmaceutical Evaluation Division, Pharmaceutical Safety and Environmental Health Bureau, Ministry of Health, Labour and Welfare dated November 28, 2017) will also be prepared.

- Attachment Form 2 (Development Status of Adverse Reactions/Infections by the Time of Approval)
- Attachment Form 12 (Development Status of Adverse Reactions/Infections in an Additional Pharmacovigilance Plan)
- Attachment Form 15 (Development Status of Adverse Reactions/Infections in Post-marketing Surveillance etc.)
- Attachment Form 16 (Summary of Patients Reported in Post-marketing Surveillance etc.)

In addition, the following documents required for periodic safety reporting (of which forms are presented in Joint PSEHB/PED Notification No. 1128-5 issued by the Director of the PDE, PSEHB, MHLW and the Director of Pharmaceutical Safety Division, PSEHB, MHLW dated November 28, 2017) will be prepared for the purpose of periodic safety reporting.

 Attachment Form 1-2 (Development Status of Adverse Reactions/Infections by the Time of Approval)

 Attachment Form 2 (Development Status of Adverse Reactions/Infections in Post-marketing Surveillance etc.)

10. APPENDICES

10.1. Appendix 1: Details of Data Handling

A1.1 Definition of Study Visits 1

For the endpoints the partial Mayo score, stool frequency subscore, rectal bleeding subscore, and physician's global assessment subscore, the study visits are defined as follows:

| Visit | Definition [time window] |
|------------------|---|
| Baseline | From 6 months before Day 1 (= the day of first dose of Xeljanz in |
| | this study = the day of the start of treatment) to Day 1 (pretreatment) |
| Week 2 | Day 2 to Day 22 |
| Week 4 | Day 23 to Day 43 |
| Week 8 | Day 44 to Day 71 |
| Week 12 | Day 72 to Day 99 |
| Week 16 | Day 100 to Day 141 |
| Week 24 | Day 142 to Day 197 |
| Week 32 | Day 198 to Day 253 |
| Week 40 | Day 254 to Day 309 |
| Week 48 | Day 310 to Day 379 |
| Week 60 | Day 380 to Day 463 |
| End of treatment | From 2 weeks before to 2 weeks after the day of last dose |
| | If the day two weeks before the last dose is Day 1 or earlier, the time |
| | window is from Day 2 to 2 weeks after the day of last dose. |

A1.2 Definition of Study Visits 2

For the endpoints the Mayo score, findings of flexible sigmoidoscopy subscore, and faecal calprotectin, the study visits are defined as follows:

[figure not shown]
| Visit | Definition [time window] |
|----------|--|
| Baseline | From 6 months (or 3 months for faecal calprotectin) before Day 1 (= |
| | the day of first dose of Xeljanz in this study = the day of the start of |
| | treatment) to Day 1 (pretreatment) |
| Week 8 | Day 2 to Day 85 |
| Week 16 | Day 86 to Day 141 |
| Week 24 | Day 142 to Day 197 |

| Visit | Definition [time window] | | |
|------------------|---|--|--|
| Week 32 | Day 198 to Day 253 | | |
| Week 40 | Day 254 to Day 309 | | |
| Week 48 | Day 310 to Day 379 | | |
| Week 60 | Day 380 to Day 463 | | |
| End of treatment | From 2 weeks before to 2 weeks after the day of last dosing | | |
| | If the day two weeks before the last dose is Day 1 or earlier, the time | | |
| | window is from Day 2 to 2 weeks after the day of last dose. | | |

10.2. Appendix 2: Example of Tabulated and Graphical Presentations of Risk Ratios Regarding the Proportion of Patients with an Adverse Reaction in Different Subgroups

| 事象名: XXXの上昇 | 区分1 | | 区分2 | | リスク | リスク比 (RR) | |
|---------------------|----------|---------|----------|-------|------|---------------|--|
| | 例数/N | (%) | 例数/N | (%) | RR | 95 %CI | |
| 性別(男性 vs. 女性) | 18/2220 | (8.0) | 3/1099 | (0.3) | 2.97 | (0.88-10.06) | |
| 65歳以上 vs. 65歳未満 | 19/2788 | 3 (0.7) | 2/531 | (0.4) | 1.81 | (0.42 - 7.74) | |
| 診断(疾患A vs.疾患B) | 3/221 | (1.4) | 18/3098 | (0.6) | 2.34 | (0.69 - 7.87) | |
| 罹病期間(1年未満 vs. 1年以上) | 9/771 | (1.2) | 7/866 | (0.8) | 1.44 | (0.54-3.86) | |
| 薬剤A 併用(あり vs. なし) | 9/798 | (1.1) | 12/2521 | (0.5) | 2.37 | (1.00 - 5.60) | |
| 薬剤A 前治療(あり vs. なし) | 1/ 148 | (0.7) | 20/3171 | (0.6) | 1.07 | (0.14-7.93) | |
| 疾患B 合併(あり vs. なし) | 16/ 1614 | 4 (1.0) | 5/1703 | (0.3) | 3.38 | (1.24-9.20) | |
| 疾患B 既往(あり vs. なし) | 7/674 | (1.0) | 14/ 2643 | (0.5) | 1.96 | (0.79 - 4.84) | |
| 肝障害(あり vs. なし) | 0/80 | | 18/2056 | (0.9) | | | |
| 腎障害(ありvs. なし) | 1/ 140 | (0.7) | 17/2004 | (0.8) | 0.84 | (0.11 - 6.28) | |

副作用XXXXの発現割合とリスク比

TRANSLATION RECORD (FOR POST-MARKETING SURVEILLANCE STUDY IN JAPAN) 10-Jan-2019

| Document Type | ゼルヤンツ錠 5mg 特定使用成績調査(潰瘍性大腸炎患者を対象とした長期使用に関する調査)統計解析計画書 | | | | |
|-----------------------------|--|---|----------|--|--|
| Document Date (Original) | 30-MAY-2022 | | | | |
| Program | A392 | Study | A3921248 | | |
| Original Language | 日本語 | Site | NA | | |
| Translation Language | 英語 | Is a back translation required? | NO | | |

FULL TRANSLATION AND REVIEW INFORMATION

| Translator Qualification Type | Translation vendor | | |
|-------------------------------|---------------------|---------------------|-------------|
| Translation Vendor | Honyaku Center Inc. | | |
| Translator Name | Honyaku Center Inc. | Date of Translation | 11-NOV-2022 |
| Reviewer Name | PPD | Date of Review | 21-NOV-2022 |
